**C4e. Sample Size, Power, and Attrition.** This trial aims to recruit a sample of 72 (36 in each group), which is a pragmatic decision based on the patient pool, budget, and two-year study period. We will recruit patients from the Health Hub and Tennessee Population Health Data Network (TN- POPnet). Given the study has broad eligibility criteria, we anticipate an estimated 20 adult patients with diabetes and obesity being eligible each month. This will provide a sufficient pool to enroll 8 patients/month and 72 patients over 9 months. We expect that after accounting for 15% attrition at 12-month follow-up, about 61 study participants will complete the study. The attrition rate is based on the evidence from our MODEL study and from Lean *et al.* This pilot study will help us to estimate the following: 1) Effect size for the study intervention, 2) Total number patients recruited, 3) Number of patients recruited each month, 4) Total time required to recruit patients, 5) Number of patients retained, and 6) Barriers and facilitators to recruitment and implementation of the interventions. The research will employ intensive *scientific rigor* in every stage of design and conduct to ensure robust and unbiased experimental design, methodology, analysis, interpretation, and reporting of results and the ability to reproduce the research findings.

**C5. Multicomponent Motivational Interventions.** All component interventions received by both the treatment and control groups will be delivered in phases as shown in **Table 2** below.

**C5a. Intensive Preparation for Change and Core Educational Interventions.** All patients will receive introductory education on plant-forward healthy eating for weight loss. Health coaches will lead two sessions (introductory and kickoff) for the treatment group; pharmacists or nutritionists will lead one traditional diabetes education session for the control group. All patients will receive evidence-based self-care tools included in the MODEL program toolkit adapted from DPP, ACT, Look AHEAD, and TARGIT, and supplemental recipe and diet information adapted from DiRECT and the Daniel Diet program. Treatment group participants will also receive training in cognitive behavioral strategies employing these tools.

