**Table 2. Study Timeline, Intervention Phases and Components, and Study Procedures**

Month(s)	Study Procedures	Treatment Group (Intervention Phases and Components)	Control Group (Intervention Phases and Components)
	Screening		
1	Baseline Visit (Randomization)	Phase 1 -Intensive Preparation for Change: 1) Two (introductory and kickoff) health coach and nutritionist or dietitian co-led support group sessions, 2) Health coaching, 3) Tailored motivational text messaging	Phase 1 -Education: One traditional diabetes education session led by a pharmacist or nutritionist/registered dietitian
2-4	Follow-up Visit 1 (Month 3)	Phase 2 -Total Diet Replacement: 1) Total diet replacement for months 2-4 using tailored healthy food boxes with recipes, 2) Health coaching, 3) Tailored motivational text messaging, 4) Coach-led support groups, 5) Monthly cooking classes, 6) Physician-supervised medication discontinuation	Phase 2 -Partial Diet Replacement: Partial diet replacement for 3 months using grocery store produce vouchers
4-6	Follow-up Visit 2 (Month 6)	Phase 3 -Food Reintroduction: 1) Health coach-led individual or group grocery store tours with individual patient reminders, 2) Health coaching, 3) Tailored motivational text messaging, 4) Coach-led support groups, 5) Monthly cooking classes	Phase 3 -Food Reintroduction: No additional activities
6-12	Follow-up Visit 3 (Month 12)	Phase 4 -Weight Loss Maintenance: 1) Health coaching, 2) Tailored motivational text	Phase 4 -Weight Loss Maintenance: No additional activities

		messaging, 3) Coach-led support groups, 4) Monthly cooking classes	
--	--	---	--

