Blood glucose will be monitored weekly at the UTHSC Health Hub months 2 through 4 (e.g., during the Total Diet Replacement phase) and periodically thereafter. Health Coaches and the UTHSC Health Hub medical director should encourage participants to continue any glucose monitoring recommended by their primary care physician or diabetes doctor and to contact their doctor and/or the UTHSC Health Hub Medical Director for blood glucose levels below 70 or above 300. Blood pressure will be monitored weekly at the UTHSC Health Hub for the 2nd – 4th months of the study (e.g., during the Total Diet Replacement phase) and periodically thereafter. Health Coaches and the UTHSC Health Hub medical director should encourage any self-monitoring recommended by their primary care physician. Advise participants to notify their healthcare provider and the Health Hub Medical Director for systolic blood pressure greater than 160 or diastolic BP greater than 100 with symptoms (acute vision changes, headache, chest pain, etc.) or systolic blood pressure greater than 180 or diastolic greater than 110 (regardless of symptoms). Advise participants to immediately call emergency medical services and seek emergent medical care for blood pressure readings 180/110 or higher AND symptoms of chest pain, shortness of breath, numbness, weakness, change in vision, difficulty speaking, or severe headache. In the three months of total diet replacement, participants should be seen at least once a week and should be offered blood glucose and blood pressure checks to assess for hyperglycemia, hypoglycemia, and/or hypertensive episodes. HEAL Diabetes Program Participant Medication Reduction/Discontinuation Instructions will be included in the intervention group's toolkits. Study personnel, including health coaches and the medical director will emphasize instructions for monitoring for adverse events related to blood pressure or blood glucose. Procedures for monitoring blood glucose and blood pressure will be included and further detailed in the Manual of Procedures (MOP).

Adverse events related to medication discontinuation are unlikely but may include hyperglycemia and hypertension. We will monitor those in the intervention group regularly for adverse events related to medication

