- [name], who is a co-investigator on this project, will have responsibility for analyzing interim data and preparing data and safety monitoring reports that the committee will review. These reports will include data on all adverse events and study outcomes for all study participants. [name] will be an ex-officio member of the committee and will not be blinded to participant group assignment. After the start of participant enrollment, we plan to conduct data and safety monitoring meetings in-person or via conference call twice a year. Data and safety monitoring reports will be sent to all committee members prior to the conference call.
- A Manual of Procedures will be developed for the study and the procedures will be strictly followed. All controlled trials personnel are trained in sessions that will cover all study procedures, including recruitment, informed consent, measurements, randomization, participant follow-up, and adverse events. Adherence to the procedures in the operations manual will be assured by periodic assessment and retraining. A co-investigator will monitor each participant for adverse events throughout the study using participant report and reports by primary care physician. All participants will be asked at each study visit about emergency visits, hospital visits, or other serious adverse events in the intervening period, and these reported events will be recorded in the study database. If significant differences in adverse events noted above are found, additional interviews of the participant experiencing these adverse events may be conducted at the discretion of the DSMB and any necessary remedial action taken will be recorded. At any point a participant may be withdrawn from the study for health-related reasons. Medical side effects of improvements in healthy eating, physical activity, and medication adherence will be explained as part of the informed consent process to each participant by trained study personnel and participants will be provided a copy of the informed consent statement that will include a written list of potential side effects prior to randomization. An attempt will be made to quantify the severity of each side effect by asking the participant to grade its importance or impact on quality of life.

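### In months 2-4 only the treatment arm has weekly scheduled safety checks, so counts of check-detected events, chiefly hyperglycemia, can look higher under treatment at equal true rates

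*Combined protocol and SAP*

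**What the plan says.** **Treatment arm.** Section C5g (PSMD Guidelines) states: "Blood glucose will be monitored weekly at the UTHSC Health Hub months 2 through 4". Blood pressure follows the same schedule, and both are checked periodically afterwards. It adds: "In the three months of total diet replacement, participants should be seen at least once a week". On harms it says: "We will monitor those in the intervention group regularly for adverse events related to medication" (the sentence goes on to discontinuation), and it names home readings as a further source of reports. C8 lists 14 coaching sessions, 6 support groups and 6 cooking classes for this arm.

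**Control arm.** Table 2 gives controls one education session and three months of produce vouchers. For Phases 3 and 4 the entry is "No additional activities". C8 sets follow-up visits for both arms at 3, 6 and 12 months. No glucose or blood-pressure check between visits is described for controls.

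**Both arms.** F2d states: "All participants will be asked at each study visit about emergency visits, hospital visits, or other serious adverse events in the intervening period". F3c repeats this and adds a concordance check against the registry. F2d and F3c also provide for co-investigator monitoring, self-report to the site, and notification by physicians and relatives. F2d gives 24-hour telephone access.

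**What reaches the DSMB.** F2d says its reports include all adverse events for all participants. F3a says only serious events are recorded and reported, but in the same sentence it names hyperglycemia as a less serious example. F2d then sets the trigger: "If significant differences in adverse events noted above are found, additional interviews of the participant experiencing these adverse events may be conducted". No test, level or threshold is attached.

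**The concern.** When one arm is checked weekly and the other is seen at long intervals, events that need a measurement to be noticed are found more often in the first arm. A raised glucose without symptoms is the clearest case. A weekly check finds it, while a question about the past three to six months may not. Extra detection under treatment and missed events among controls push the comparison in the same direction, towards apparent harm from the intervention.

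F2d asks the DSMB for the risk-to-benefit profile and lets it recommend changes to any component of the trial. Hyperglycemia is named as recorded in F3a and as a potential intervention-related event in F3b. A table of all events by arm, with no note of how each was found, would invite a causal reading that it cannot support. Nothing in the plan restricts the comparison to events found the same way in both arms or mentions unequal surveillance.

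**Working it through.** **1. The plan's own figure.** The documents give no adverse-event figure for this comparison. The nearest stated figure is the number of completers. C4e says "This trial aims to recruit a sample of 72 (36 in each group" and "after accounting for 15% attrition at 12-month follow-up, about 61 study participants will complete the study". Check: 72 × (1 − 0.15) = 61.2, which agrees.

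**2. Scheduled contacts.**
- Months 2-4: about 13 weekly checks in the treatment arm (13/52 = 25% of the year). Controls have one visit in the window, at month 3, which the treatment arm has as well.
- Twelve months, treatment: 13 + 3 follow-up visits = 16 if coaching, groups and classes coincide with the weekly checks. If none coincide, 13 + 14 + 6 + 6 + 3 = 42.
- Twelve months, control: 3 follow-up visits + 1 education session = 4.

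**3. Apparent ratio within months 2-4, at equal true rates.** Assume full capture at weekly checks and recall r at visits, with r = 0.5 to 0.7. Neither assumption is in the documents.
- Ratio = 1/r: 1/0.7 = 1.4 and 1/0.5 = 2.0.

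**4. Apparent ratio over 12 months.** Assume also that events are evenly spread and that there is no extra detection after month 4.
- Ratio = (0.25 × 1 + 0.75 × r)/r.
- r = 0.7: (0.25 + 0.525)/0.7 = 1.11.
- r = 0.5: (0.25 + 0.375)/0.5 = 1.25.
- Clustering of events in months 2-4, or detection at later coaching contacts, would raise these values.

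**5. Chance of a falsely significant difference.** This illustration uses 36 per arm, equal true risk, exact binomial enumeration and a two-sided Fisher test at p < 0.05. Detection is assumed to be 90% under treatment. The test and level are also assumed, since the plan states none.

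| True risk | Control detection 90% (ratio 1.0) | 60% (ratio 1.5) | 45% (ratio 2.0) |
|---|---|---|---|
| 5% | 0.002 | 0.002 | 0.002 |
| 20% | 0.025 | 0.059 | 0.113 |
| 30% | 0.027 | 0.095 | 0.210 |

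The problem therefore needs a fairly common event. For rare events the test almost never fires.

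**6. Severe hypoglycemia.** F3b cites 0.2 to 0.57 per 100 patient-years. With 36 patient-years (full follow-up of the treatment arm), the expected count is 36 × 0.2/100 = 0.07 to 36 × 0.57/100 = 0.21 events. A significant difference in that event is very unlikely with or without surveillance bias.

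**The case against.** The strongest reply is that the plan already provides a common system. Every participant gets the same question at the same visits. Between visits, self-report, physician and relative notification, co-investigator monitoring and telephone access apply to both arms. A reader might infer from Table 2 that control harms are looked for only at study visits. The documents do not support that: the entry for Phases 3 and 4 describes intervention content, not safety follow-up. What is limited to visits in controls is scheduled, active ascertainment.

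A reader might also infer that the DSMB trigger itself rests on biased counts. Its wording refers to events noted above, and the nearest such events are emergency visits, hospital visits and other serious events from the common question. For those, the imbalance matters much less. The stated consequence is optional interviews and recorded remedial action, with no stopping rule attached.

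Three further points stand. The weekly contacts are glucose and blood-pressure checks to be offered, not adverse-event interviews. F3a may keep most non-serious events out of the record. The Manual of Procedures, which is not among the documents, may add detail. Table 3 also lists weekly body weight without naming an arm, but that does not clearly give controls weekly safety checks.

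These points narrow the concern without removing it. Voluntary reporting does not find an asymptomatic high reading. The passive channels are also prompted more in the treatment arm: C5g gives toolkit instructions and encourages an early primary-care visit to assess glucose and blood pressure. F2d still sends all adverse events to the DSMB, and F3a names hyperglycemia as recorded.

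**Conclusion.** The concern holds for non-hospital events that a scheduled check would detect, chiefly hyperglycemia. Their counts can look higher in the treatment arm when true rates are equal. Serious events from the common visit question are much less affected.

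The size is an assumption, not a finding from the documents. With full weekly capture and 50-70% recall, the ratio is 1.4-2.0 inside months 2-4. Over 12 months it is about 1.1-1.25, given evenly spread events and no extra detection later. Reading 1.4-2.0 as the bias for the whole trial would be wrong on those assumptions, because the weekly schedule covers about a quarter of the year. Nor do the documents support calling the risk-benefit assessment uninterpretable: F3b and the paragraphs that follow it classify events by relationship, severity and expectedness, and the DSMB sees all pertinent data. This is a reporting weakness that should be corrected because the correction is cheap.

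**What to change.** 1. Add an ascertainment-source field to the event form: study-visit question, registry or record search, weekly check, coaching contact, home reading, or participant, relative or physician report.
2. In F2d, F3c and the final report, base the main between-arm comparison on events elicited by the identical question at the 3-, 6- and 12-month visits, plus a registry or record search applied in the same way to both arms.
3. List events found only at weekly checks, coaching contacts or home readings separately by arm, next to an all-events table, so that no harm is dropped from view.
4. Reconcile F2d (all adverse events) with F3a (serious events, plus hyperglycemia described as less serious), so that the form, the DSMB report and the final report count the same things.

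Expedited safety handling and the monitoring itself stay unchanged. The cost is one REDCap field, a change to the table shells and a wording correction. The main comparison will contain fewer events. Treatment harms caught and corrected at a weekly check may appear only in the separate listing, which is why the all-events table must sit beside it.

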- All participants will be encouraged to contact the study site if any episodes of severe hypoglycemia, hyperglycemia, or hospitalizations of any nature occur. In addition, physicians will be asked to notify the study site of any hospitalizations or severe episodes of hypoglycemia or hyperglycemia. Conversely, if the UTHSC Health Hub personnel uncover a morbid event in a study participant, the study staff will contact the participant's personal health care provider. The participants will have access to study personnel or to one of the physician investigators by telephone 24 hours each day through the on-call system in the event of medical problems related to the study. Our health systems have on-call systems that give the participants access to a physician investigator 24 hours a day. To further ensure participant safety, during the follow-up period we plan to assess wellbeing by physical assessment including blood pressure.

**F3a. Adverse Events.** We define serious adverse events as any adverse event or adverse reaction that results in death, is life-threatening, requires hospitalization or prolongation of existing hospitalization, results in persistent or significant disability or incapacity, or congenital anomaly or birth defect. We define adverse events as any untoward medical occurrence in a participant or experimental investigation subject administered a study treatment and which does not necessarily have a causal relationship with this treatment. Because this is a pragmatic trial with minimal risks we will only be recording and reporting serious adverse events such as severe hypoglycemia, or less serious, hyperglycemia.

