**F3b. Classification of Events.** In this study, the likelihood of serious adverse events associated with the planned interventions is very low, and mostly consists of a small possibility of serious hypoglycemic or hyperglycemic reactions associated with improvements in health habits as detailed below. All adverse events will be classified as to whether they are serious or not serious. An adverse event is considered serious if it is life threatening, prolonged or permanently disabling, requires or prolongs hospitalization for any cause other than routine delivery, is a congenital anomaly, or a major cardiovascular event. An event may also be considered serious if an investigator judges it to be a significant hazard or contraindication to continued study intervention or use of study medication. In addition, we will classify all adverse events regarding the relationship, severity, and expectedness as described below.

**Relationship** The following are expected adverse events that may occur during the trial:

**Related to Intervention.** Potential adverse events (AE) known to be associated with caloric restriction, weight loss, or improved medication adherence in patients with diabetes: hypoglycemia, hyperglycemia, malnutrition, bone loss, gall bladder disease. The DiRECT trial which employed a similar intervention found that severe hypoglycemia occurred between 0.2 to 0.57 times per 100 patient years in the treatment arm over the first 4 years of the study. Potential AE's known to be associated with exercise in patients with diabetes: hypoglycemia, fracture or other injury, cardiac arrhythmia, cardiovascular event.

**Related to condition under study.** Potential AE's known to be associated with overweight or obesity include: diabetes, hypertension, dyslipidemia, cardiovascular disease (CVD), gall bladder disease, liver disease. All patients will be monitored at every data collection visit through the 12-month visit for the occurrence of these adverse events.

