**Severity** During the trial participants will be queried to determine if a serious adverse event has occurred as described above and all adverse events will be identified through patient and provider report. All serious adverse events will be recorded. A serious adverse event is considered serious if it is life threatening, prolonged or permanently disabling, requires or prolongs hospitalization for any cause other than routine delivery, is a congenital anomaly, a major cardiovascular event, or cancer other than non-melanoma skin cancer. An event may also be considered serious if an investigator judges it to be a significant hazard or contraindication to continued study intervention or use of study medication.

**Expectedness** Adverse events will also be classified as to whether they are expected or unexpected. An unexpected adverse event is one for which the nature or severity is not consistent with information about the condition under study or intervention in the protocol, consent form, or program brochure. An expected event is one known to be associated with the intervention or condition under study. Thus, expectedness is related both to the intervention and to the condition under study. All serious or unexpected adverse events related to the intervention will be reported to the IRB and to the sponsor in a timely manner.

**F3c. Data Collection Procedures for Adverse Events.** As described above, a co-investigator will monitor each participant for serious adverse events throughout the study using participant and provider reports. All patients will be asked at each study visit about emergency visits, hospital visits, or other serious adverse events in the intervening period, and these reported events will be recorded in the study database and concordance with the registry assessed as described above. Participants will be asked at each study visit about any serious adverse events that may have occurred between study visits. All participants will be encouraged to contact the study site if untoward symptoms, illnesses, or hospitalizations of any nature occur. In addition, their relatives and their personal physicians will be asked to notify the study site of any hospitalizations or major illnesses. Conversely, if the health hub personnel uncover a morbid event in a study participant, the study staff will contact the participant's personal health care provider.

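### F3a limits adverse event recording to serious events, which cannot be squared with the classification rule in F3b or the IRB and sponsor reporting rule under Expectedness, and the protocol defines a serious event in three ways

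*Combined protocol and SAP*

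**What the plan says.** **Recording limited to serious events.** F3a gives the reason (a pragmatic trial with minimal risks) and then the rule: "we will only be recording and reporting serious adverse events such as severe hypoglycemia, or less serious, hyperglycemia". The Severity paragraph of F3b adds "All serious adverse events will be recorded" and does not mention recording others. Sections F and F1a set out what is recorded for a serious event and are likewise silent on the rest.

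**Wider commitments.**
- F3b: "All adverse events will be classified as to whether they are serious or not serious", and further, "we will classify all adverse events regarding the relationship, severity, and expectedness as described below".
- F3b, on events related to the condition under study: "All patients will be monitored at every data collection visit through the 12-month visit for the occurrence of these adverse events".
- F3b, Severity: "all adverse events will be identified through patient and provider report".
- F3b, Expectedness: "All serious or unexpected adverse events related to the intervention will be reported to the IRB and to the sponsor in a timely manner".
- F2d, on the DSMB reports: "These reports will include data on all adverse events and study outcomes for all study participants".

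**Visit questions.** F2d and F3c ask participants at each study visit about emergency visits, hospital visits and other serious events, and place the answers in the study database.

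**Reporting period.** The section on the adverse event reporting period runs it from May 1, 2023 to March 30, 2024.

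**The concern.** In the treatment arm, C5g has diabetes and antihypertensive drugs stopped or reduced when the low-calorie diet begins. F2c accepts that the intervention may raise the risk of hypoglycemic or hyperglycemic episodes. F2d asks the DSMB to weigh risk against benefit and provides for follow-up interviews if adverse events differ significantly.

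Much of the harm to be expected from this intervention would fall short of serious. If staff follow F3a, those events do not enter the adverse event record. The DSMB reports, and the six-monthly safety reports to the IRB, would then be silent on them. If some staff follow F3a and others follow F3b, the record is filled by two rules and counts by arm become hard to interpret.

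Even a trial that records only serious events needs a single definition of serious, because that definition then decides what is recorded.

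**Working it through.** No alpha, power or rate enters this point. The check is to follow specimen events through each rule, compare the definitions, and check the dates.

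**Step 1. Specimen events.**

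| Event | F3a | Other sections | Result |
|---|---|---|---|
| Non-serious, unexpected, related to the intervention; no emergency or hospital visit | Not recorded or reported | Expectedness: goes to IRB and sponsor. F3b: classified | Contradiction |
| Non-severe hypoglycemia; no emergency or hospital visit | Not recorded | F3b lists hypoglycemia among the events that may occur and classifies all events; Severity says all are identified | Contradiction on classification; lost to the record under F3a |
| Symptomatic low blood pressure; no emergency or hospital visit | Not recorded | C5g names low blood pressure as something to look for at primary care follow-up; F3b classifies all events | As above |
| Non-serious event with an emergency visit but no admission | Not recorded | F2d and F3c: reported emergency visits go into the database | Captured |
| Hyperglycemia short of serious | Apparently admitted, but the wording is unclear | F3b: classified | Ambiguous |

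The Expectedness rule is the clearest conflict. It joins serious and unexpected by *or*, so an event can qualify without being serious. F3a covers reporting as well as recording, so both sentences cannot be followed.

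**Step 2. Definitions of serious.**

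| Criterion | F3a | F3b, opening | F3b, Severity |
|---|---|---|---|
| Death named | Yes | No | No |
| Life-threatening, disability, hospitalization, congenital anomaly | Yes | Yes (routine delivery excepted) | Yes (routine delivery excepted) |
| Major cardiovascular event | No | Yes | Yes |
| Investigator judgement | No | Yes | Yes |
| Cancer (non-melanoma skin cancer excepted) | No | No | Yes |

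A cancer diagnosed without admission is serious under Severity but does not clearly meet the other two definitions.

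**Step 3. Other routes to the DSMB.** Blood pressure is a primary outcome in Table 3 and is among the data listed in section E, so readings reach the DSMB as study outcomes. The weekly glucose readings described in C5g appear neither in Table 3 nor in section E. C1c names fasting glucose only at baseline and 12 months.

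**Step 4. Reporting period.** Enrollment starts on May 1, 2023, so the first visit one year later falls at about May 1, 2024. If month 12 is counted with baseline as month 1, as Table 2 might be read, the earliest date is May 1, 2023 + 11 months = April 1, 2024. Both are after March 30, 2024. No 12-month visit falls inside the period, although F3b monitors through that visit.

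**The case against.** **Limited recording is a stated choice with a reason.** This stands. Recording only serious events can be reasonable in a small pilot, and a reader should not infer that F3a is wrong in itself. The fault is that other sections promise something else.

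**The authors may use the terms loosely.** F2d refers back to adverse events just after listing emergency visits, hospital visits and serious events. F3c speaks of serious adverse events where F2d, in an otherwise similar sentence, says adverse events. On this reading, the DSMB reports cover all *recorded* events and the conflict with F2d eases. It does not help F3b, which sorts events into serious and not serious, or the Expectedness rule, which separates serious from unexpected.

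**Non-serious events are partly captured.** This also stands, and it limits the point. A reader might infer that nothing short of serious is ever recorded, or that the DSMB would see no blood pressure data. The documents do not support either: reported emergency and hospital visits are recorded, and blood pressure is an outcome.

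**The Manual of Procedures may settle it.** F2d says it will be strictly followed, and C5g leaves monitoring detail to it. It is not among the documents, and whatever it says, the protocol's own sentences would still disagree.

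It is also tempting to size the gap by counting the event types listed in F3b or the weekly checks. Neither count measures it. F3b introduces its list as expected events, so the list says little about unexpected ones. The weekly checks bear on unequal detection between arms, which is a separate matter.

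**Conclusion.** The conflict holds as a matter of text. F3a cannot be reconciled with the classification of all adverse events in F3b or with the reporting of serious or unexpected related events under Expectedness. It fits F2d only if the DSMB reports are read as covering recorded events. Serious is defined in three non-identical ways, and the hyperglycemia wording in F3a is unclear.

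The size is limited to non-serious events that lead to no emergency or hospital visit. How many there would be cannot be estimated from the documents. The efficacy analyses are not affected; the safety record and its comparison by arm are. This should be corrected. The conclusion assumes that staff would apply F3a as written.

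**What to change.** Reconcile sections F, F1a, F2d and F3a to F3c to one recording scope and one definition of serious, and clarify the hyperglycemia wording in F3a.

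**Preferred scope.** In both arms, record at study visits, whatever the seriousness:
- the events named in F3b and the medication-discontinuation events named in C5g, if new or worse since baseline;
- low blood pressure, which C5g also mentions;
- any other event judged unexpected and related to the intervention.

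Then align the visit questions in F2d and F3c, and the references to all adverse events in F2d and F3b (including Severity), with that scope. Extend the reporting period so that it covers monitoring through the 12-month visit. In DSMB tables, show events found at the treatment-arm weekly checks separately from those found at study visits in both arms.

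**Alternative.** If recording only serious events is kept, narrow F2d, F3b and F3c to match. State in the DSMB, IRB and final reports that non-serious events were not systematically collected. The single definition of serious and the corrected reporting period are still needed.

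**Cost.** The preferred scope needs wording changes and one short REDCap form at up to 72 × 3 = 216 follow-up visits (61 × 3 = 183 if only the expected completers are counted), plus entries from the weekly checks. Some events listed in F3b, such as bone loss and liver disease, have no measure in Table 3 and would be captured by report only. Detection stays unequal between arms, which is why the two sources are shown apart. The alternative costs wording only, but leaves the DSMB without systematic data on non-serious events. Neither option changes a clinical management rule.
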